### **6.8.1 Acceptable concomitant medications**

All treatments that the Investigator considers necessary for a participant's welfare may be administered at the discretion of the Investigator in keeping with the community standards of medical care. All concomitant medication will be recorded on the e-CRF including all prescription, OTC, herbal supplements, and IV medications and fluids. If changes occur during the trial period, documentation of route, and date will also be included on the e-CRF.

Palliative and supportive care is permitted during the course of the trial for underlying medical conditions and management of symptoms. Surgery or radiotherapy for tumor control is not permitted during the study; however, radiotherapy or procedures for symptom management is allowed after discussion with and approval by the Sponsor.

All concomitant medications received within 28 days before the first dose of trial treatment through the Follow-up Visit should be recorded.

### *Colony-Stimulating Factors*

Routine use of colony-stimulating factors (CSFs) is not permitted. American Society of Clinical Oncology guidelines for use of CSFs should be followed (28).

## **6.8.2 Prohibited concomitant medications**

Participants are prohibited from receiving the following therapies during the Screening and Treatment Period of this trial:

- Antineoplastic systemic chemotherapy or biological therapy not specified in this protocol.
- Immunotherapy not specified in this protocol.
- Investigational agents other than specified in this protocol.
- Radiotherapy for tumor control (please refer to [Section 6.8.1](#) for allowed radiotherapy).
- Live or live-attenuated virus vaccines within 28 days prior to the first dose of trial treatment and while participating in the trial. Examples of live-virus vaccines include, but are not limited to, the following: measles, mumps, rubella, chickenpox, yellow fever, seasonal flu (seasonal flu vaccines that do not contain live virus are permitted), nasal H1N1 flu, rabies, Bacillus Calmette-Guérin (BCG), and typhoid.
- Systemic glucocorticoids and other immunosuppressive therapies such as anti-TNF, anti-IL6, etc, except for:
  - Treatment of immune-mediated AEs when indicated (IRR, CRS, irAE, and ICANS, see individual substudies protocols in [Section 6.5](#)),
  - Treatment of any life-threatening emergency,
  - Physiologic replacement as long as they are not being administered for immunosuppressive intent, and
  - A brief course ( $\leq 7$  days) of systemic corticosteroid for prophylaxis (eg, contrast dye allergy) or for the treatment of non-autoimmune conditions (eg, delayed-type hypersensitivity reactions caused by contact allergen).

Participants who, in the assessment by the Investigator, require the use of any of the aforementioned treatments for clinical management should be removed from the trial. Participants may receive other medications that the Investigator deems to be medically necessary.

The exclusion criteria describe other medications which are prohibited in this trial.

There are no prohibited therapies during the Observation and Survival Follow-up Periods.

For withholding antihypertensive medications as part of hydration guidelines, please refer to [Section 6.1.3](#).

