## **6.8 CONCOMITANT THERAPY**

Any medication (including over-the-counter [OTC] or prescription medicines, vitamins, and/or herbal supplements) or vaccine that the participant is receiving at the time of enrollment or receives during the study must be recorded along with:

- Reason for use.
- Dates of administration including start and end dates.

The Sponsor should be contacted if there are any questions regarding concomitant or prior therapy.

Medications or vaccinations specifically prohibited in the exclusion criteria are not allowed during the ongoing trial. If there is a clinical indication for any medication or vaccination specifically prohibited during the trial, discontinuation from study intervention may be required. The Investigator is to discuss prohibited medication/vaccination with the Sponsor. The final decision on any supportive therapy or vaccination rests with the Investigator and/or the participant's primary physician. However, the decision to continue the participant on trial therapy schedule requires the mutual agreement of the Investigator, the Sponsor and the participant.

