## 7 DISCONTINUATION OF STUDY INTERVENTION AND PARTICIPANT DISCONTINUATION/WITHDRAWAL

### 7.1 DISCONTINUATION OF STUDY INTERVENTION

#### 7.1.1 Permanent discontinuation

Study intervention should be permanently discontinued in any of the following cases:

- At the participant's request, at any time and irrespective of the reason (consent's withdrawal), or at the request of their legally authorized representative (if allowed by local regulations). "Legally authorized representative" is considered to be an individual or judicial or other body authorized under applicable law to consent on behalf of a prospective participant to the patient's participation in the procedure(s) involved in the research.
- If, in the Investigator's opinion, continuation of the study treatment would be detrimental to the participant's wellbeing, such as:
  - Unacceptable AE.
  - Documented disease progression
  - Poor compliance to the study protocol.
  - Completion of 35 cycles when applicable
  - Other, such as concurrent illness, that prevents further administration of study intervention, or that in the Investigator's opinion, in the best interest of the participant
- In case of pregnancy occurrence.

If study intervention is permanently discontinued, the participant will remain in the study to be evaluated for serial tumor assessment if permanent discontinuation is not due to PD, for safety assessment as per SoA ([Section 1.3](#)) and until resolution or stabilization of AE, and any other assessment as per SoA. Data to be collected at the time of discontinuation of study intervention and follow-up and for any further evaluations that need to be completed are reported in the SoA.

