### **Handling of participants after permanent intervention discontinuation**

Participants will be followed-up according to the study procedures specified in this protocol up to the scheduled date of study completion, or up to recovery or stabilization of any AE to be followed-up as specified in this protocol, whichever comes last.

If possible, and after the permanent intervention discontinuation, the participants will be assessed using the procedure normally planned for the last dosing day with the IMP including a pharmacokinetics sample, if appropriate. Tumor assessment should be repeated if not done at the last cycle. A biopsy (optional - special consent) may be performed if treatment is discontinued for disease progression following an initial response.

All cases of permanent intervention discontinuation must be recorded by the Investigator in the appropriate pages of the e-CRF when considered as confirmed.

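### Section 6.8.2 takes participants who need a prohibited treatment off the trial, whereas 6.8 and 7.1.1 at most stop study treatment and keep them in follow-up

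*Protocol*

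**What the plan says.** Master protocol 6.8.2 lists therapies barred during screening and treatment. The list mixes anticancer treatments (chemotherapy, biologics, immunotherapy, radiotherapy for tumor control) with others: live vaccines, systemic glucocorticoids and other immunosuppressants outside the stated exceptions, and "Investigational agents other than specified in this protocol". Participants judged by the Investigator to "require the use of any of the aforementioned treatments for clinical management should be removed from the trial". The section closes: "There are no prohibited therapies during the Observation and Survival Follow-up Periods".

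Other sections deal with the same or the neighbouring situation:

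- **6.8:** where a prohibited medication or vaccination is clinically indicated, "discontinuation from study intervention may be required". Continuing is also possible: "the decision to continue the participant on trial therapy schedule requires the mutual agreement of the Investigator, the Sponsor and the participant".
- **7.1.1:** "If study intervention is permanently discontinued, the participant will remain in the study to be evaluated for serial tumor assessment", provided the reason for stopping was not PD. Safety assessment continues as well.
- **Handling after permanent discontinuation:** "Participants will be followed-up according to the study procedures specified in this protocol up to the scheduled date of study completion", or until AEs recover or stabilize if that is later. Also: "Tumor assessment should be repeated if not done at the last cycle".
- **7.2:** leaving the study is a separate act. It ends both treatment and study participation and rules out re-inclusion. The Investigator may decide it on grounds of safety, behavior or compliance, and it is expected to be uncommon. Participants who stop IMP are encouraged to stay.
- **8.3.1 (master and Substudy 01):** SAEs and AESIs are collected to 90 days after last dose. In Cohort A1, immune-related AEs are also collected to 90 days, whether or not another anticancer therapy has started.

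**The concern.** For a participant on treatment, the sites have two different instructions for one event. Under 6.8 the participant may stop study treatment, or may even continue by agreement, and 7.1.1 then sets the follow-up. Under 6.8.2 the participant leaves the trial. Section 7.2 keeps stopping treatment and leaving the study apart, so the difference matters in practice.

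A literal reading puts two things at stake. The first is post-treatment safety collection, whichever listed treatment is involved. The second is tumor follow-up, but only where the treatment is not an anticancer therapy. In that case a participant with a first CR or PR could be withdrawn before the confirmatory scan. That participant would then count as a non-responder on the primary endpoint, although the protocol's own follow-up would have scanned them.

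**Working it through.** **1. Instructions side by side, participant on treatment**

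| Source | Study treatment | Study participation |
|---|---|---|
| 6.8 | may have to stop; may continue by agreement | not ended |
| 6.8.2 | ends | ends, if read literally |
| 7.1.1 and handling text | has stopped | continues, with follow-up |
| 7.2 | ends | ends; discretionary and expected to be uncommon |

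6.8 and 6.8.2 address the same event and differ. During screening there is no conflict: a participant who is not subsequently enrolled is a screen failure (5.4).

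**2. What is at risk, by type of treatment**

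- *Any listed treatment:* SAE and AESI collection to 90 days and, in Cohort A1, immune-related AE collection to 90 days. Section 8.3.1 has no stop at the start of another anticancer therapy. Survival calls (4.1) are also affected.
- *New anticancer therapy:* little changes for tumor endpoints. Imaging already ends (4.1, 8.1.1), the BOR window closes (9.4.2) and PFS is censored (9.4.3.4).
- *Not an anticancer therapy:* a vaccine or steroid does not close the BOR window, so a later confirmatory scan would count. After a stop without PD, imaging runs every 3 months (4.1). Withdrawal would cut off that imaging and with it later PFS and DoR assessments.

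**3. When a first response would go unconfirmed**

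Confirmation needs a second assessment at least 4 weeks (28 days) after the first (9.4.2). Two scans around discontinuation could supply it: the repeat assessment in the handling text, and the CT/MRI marked in the SoA at the EOT visit, 30 (±7) days after last IMP. Either confirms only if it falls 28 days or more after the first response.

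- First response and last dose on the same day, for example Day 63: the EOT scan falls 23 to 37 days later. From day 28 to day 37 it can confirm; from day 23 to day 27 it cannot.
- First response on Day 63, last dose at Cycle 3 Day 1 (Day 42, undelayed 21-day cycles): the EOT visit is at 42 + 30 = Day 72, which is 72 − 63 = 9 days after the response (2 to 16 with the window). This is too early. Taking 3 months as 91 days, Follow-up Visit 1 is at 42 + 91 = Day 133, which is 70 days after the response. It would confirm, but it is lost if the participant has been withdrawn.

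A participant with a first CR or PR already has an evaluable post-baseline assessment. They therefore stay in the efficacy population (Table 6) and count in the denominator as a non-responder.

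**4. Size of one such case**

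Exact 90% limits for x responders of n: lower = Beta quantile (0.05; x, n − x + 1), upper = Beta quantile (0.95; x + 1, n − x). For n = 40, both rows reproduce Table 5:

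- x = 8: 20.0% (10.4% to 33.2%)
- x = 7: 17.5% (8.5% to 30.4%)

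The difference is 1/40 = 2.5 points.

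For safety, the protocol's chance of seeing at least one event of 5% incidence is 1 − 0.95^40 = 87.1%. Dropping one participant altogether gives 1 − 0.95^39 = 86.5%. This overstates the loss, because events before withdrawal are still recorded.

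**The case against.** The best defense is that nobody would read the sentence literally. It serves screening and treatment together, and leaving the trial is right in screening. The parent section, 6.8, speaks of stopping study intervention, and 7.1.1 then keeps the participant in the study. The closing line about the Observation and Survival Follow-up Periods also suggests that stopping treatment was meant. This shows the likely intent, but the instruction in 6.8.2 still says something else. Section 7.2 leaves withdrawal to discretion and expects it rarely; 6.8.2 directs it.

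A reader might also infer more than the documents support:

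- *That 7.1.1 forbids withdrawal.* It does not. Section 7.2 lets the Investigator withdraw a participant on safety, behavior or compliance grounds, and needing a barred drug could fall there.
- *That the Observation-period line is a further contradiction.* Participants reach that period by other routes, such as PD, AEs or completing 35 cycles. The line is evidence of intent only.
- *That any removal within 28 days of a first response loses it.* The EOT scan can fall at 28 days or later, as shown in the working.
- *That safety data are certainly lost.* 8.3.1 makes no exception for removed participants, and 7.2 refers sites to the SoA for data at study discontinuation and follow-up.
- *That a survival endpoint suffers.* Overall survival is not among the visible primary or secondary endpoints, and the Sponsor may cancel survival calls at any time.

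The affected group is also narrow. Treatment of IRR, CRS, irAEs and ICANS, life-threatening emergencies, physiologic replacement, and steroid courses of up to 7 days for prophylaxis or non-autoimmune conditions are all exempt.

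**Conclusion.** The sentence is wrong as written, and the point is minor. For participants on treatment, 6.8.2 conflicts with 6.8 and does not fit the follow-up in 7.1.1 and the handling text. Any harm depends on a site taking 6.8.2 literally.

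If that happens, up to 90 days of SAE and AESI collection, and of irAE collection in Cohort A1, is at risk for each participant withdrawn. Where the treatment is not an anticancer therapy, confirmation of a first response and later PFS and DoR imaging are also at risk, unless a discontinuation or EOT scan falls at least 4 weeks after the response. Each responder lost costs 2.5 ORR points at N=40. That is the cost of one case, not an estimate of the total effect, and the confidence intervals are descriptive because no hypothesis is tested. The documents give no frequency; the number affected is probably small.

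**What to change.** In 6.8.2, replace the removal instruction for participants on treatment with: *should be discontinued from study treatment (subject to Section 6.8) and followed per Sections 4.1, 7.1.1 and the SoA; withdrawal from the study occurs only per Section 7.2.* Add: *Participants still in screening are screen failures (Section 5.4).*

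The cost is two sentences in the next amendment. No visits are added, because this follow-up is already scheduled for every participant who stops treatment.

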## 7 DISCONTINUATION OF STUDY INTERVENTION AND PARTICIPANT DISCONTINUATION/WITHDRAWAL

### 7.1 DISCONTINUATION OF STUDY INTERVENTION

#### 7.1.1 Permanent discontinuation

Study intervention should be permanently discontinued in any of the following cases:

- At the participant's request, at any time and irrespective of the reason (consent's withdrawal), or at the request of their legally authorized representative (if allowed by local regulations). "Legally authorized representative" is considered to be an individual or judicial or other body authorized under applicable law to consent on behalf of a prospective participant to the patient's participation in the procedure(s) involved in the research.
- If, in the Investigator's opinion, continuation of the study treatment would be detrimental to the participant's wellbeing, such as:
  - Unacceptable AE.
  - Documented disease progression
  - Poor compliance to the study protocol.
  - Completion of 35 cycles when applicable
  - Other, such as concurrent illness, that prevents further administration of study intervention, or that in the Investigator's opinion, in the best interest of the participant
- In case of pregnancy occurrence.

If study intervention is permanently discontinued, the participant will remain in the study to be evaluated for serial tumor assessment if permanent discontinuation is not due to PD, for safety assessment as per SoA ([Section 1.3](#)) and until resolution or stabilization of AE, and any other assessment as per SoA. Data to be collected at the time of discontinuation of study intervention and follow-up and for any further evaluations that need to be completed are reported in the SoA.

#### **7.1.1.1 Unacceptable adverse events leading to permanent intervention discontinuation**

Discontinuation of study intervention for abnormal liver function should be considered by the Investigator when a participant meets one of the conditions outlined in the dose modification and toxicity management guidelines (see individual substudies protocols) or if the Investigator believes that it is in best interest of the participant.

If a clinically significant finding is identified after enrollment, the Investigator or qualified designee will determine if the participant can continue in the study and if any change in participant management is needed. This review of the electrocardiogram (ECG) printed at the time of collection must be documented. Any new clinically relevant finding should be reported as an AE.

Any potentially clinically significant abnormal laboratory value or ECG parameter will be immediately rechecked for confirmation and repeated after 24 hours to document evolution before making a decision of permanent intervention discontinuation for the concerned participant.

Decision criteria for discontinuation following immune-mediated AEs are described in Section 6.5 of individual substudies protocols (Guidelines for the management of IRR, CRS, ICANS, VLS).

If participants are clinically stable, and possibly deriving clinical benefit from therapy with minimal toxicity, they will be maintained on treatment.

See the SoA for data to be collected at the time of intervention discontinuation and follow-up and for any further evaluations that need to be completed.

### **Handling of participants after permanent intervention discontinuation**

Participants will be followed-up according to the study procedures specified in this protocol up to the scheduled date of study completion, or up to recovery or stabilization of any AE to be followed-up as specified in this protocol, whichever comes last.

If possible, and after the permanent intervention discontinuation, the participants will be assessed using the procedure normally planned for the last dosing day with the IMP including a pharmacokinetics sample, if appropriate. Tumor assessment should be repeated if not done at the last cycle. A biopsy (optional - special consent) may be performed if treatment is discontinued for disease progression following an initial response.

All cases of permanent intervention discontinuation must be recorded by the Investigator in the appropriate pages of the e-CRF when considered as confirmed.

#### **7.1.2 Temporary discontinuation**

Temporary intervention discontinuation may be considered by the Investigator because of suspected AEs or disruption of the clinical trial due to a regional or national emergency declared by a governmental agency ([Section 10.11](#)). For all temporary intervention discontinuations, duration should be recorded by the Investigator in the appropriate pages of the e-CRF.

#### **7.1.3 Rechallenge**

Re-initiation of intervention with the IMP will be done under close and appropriate clinical/and or laboratory monitoring once the Investigator will have considered according to his/her best medical judgment that the responsibility of the IMP in the occurrence of the concerned event was unlikely and if the selection criteria for the study are still met.

Recommendations for rechallenge in the context of an epidemic/pandemic (eg, COVID-19), are included in the Contingency Measures for a regional or national emergency that is declared by a governmental agency ([Section 10.11](#)).

## 7.2 PARTICIPANT DISCONTINUATION/WITHDRAWAL FROM THE STUDY

- A participant may withdraw from the study at any time at his/her own request, or may be withdrawn at any time at the discretion of the Investigator for safety, behavioral or compliance reasons. This is expected to be uncommon.
- At the time of discontinuing from the study, see SoA for data to be collected at the time of study discontinuation and follow-up and for any further evaluations that need to be completed.
- The participant will be permanently discontinued both from the study intervention and from the study at that time.
- If the participant withdraws consent for disclosure of future information, the Sponsor may retain and continue to use any data collected before such a withdrawal of consent.
- If a participant withdraws from the study, he/she may request destruction of any samples taken and not tested, and the Investigator must document this in the site study records.

If participants no longer wish to take the IMP, they will be encouraged to remain in the study.

The Investigators should discuss with them key visits to attend. The value of all their study data collected during their continued involvement will be emphasized as important to the public health value of the study.

Participants who withdraw from the study intervention should be explicitly asked about the contribution of possible AEs to their decision, and any AE information elicited must be documented.

All study withdrawals should be recorded by the Investigator in the appropriate screens of the CRF and in the participant's medical records. In the medical record, at least the date of the withdrawal and the reason should be documented.

In addition, a participant may withdraw his/her consent to stop participating in the study. Withdrawal of consent for intervention should be distinguished from withdrawal of consent for follow-up visits and from withdrawal of consent for non-participant contact follow-up, eg, medical record checks. The site should document any case of withdrawal of consent.

Participants who have withdrawn from the study cannot be re-included in the study. Their inclusion and intervention numbers must not be reused.

## 7.3 LOST TO FOLLOW UP

A participant will be considered lost to follow-up if he or she repeatedly fails to return for scheduled visits and is unable to be contacted by the study site.

The following actions must be taken if a participant fails to return to the clinic for a required study visit:

- The site must attempt to contact the participant and reschedule the missed visit as soon as possible and counsel the participant on the importance of maintaining the assigned visit schedule and ascertain whether or not the participant wishes to and/or should continue in the study.
- Before a participant is deemed lost to follow-up, the Investigator or designee must make every effort to regain contact with the participant (where possible, 3 telephone calls and, if necessary, a certified letter to the participant's last known mailing address or local equivalent methods). These contact attempts should be documented in the participant's medical record.
- Should the participant continue to be unreachable, he/she will be considered to have withdrawn from the study.

Discontinuation of specific sites or of the study as a whole are handled as part of Appendix 1 ([Section 10.1](#)).

